23.3.2 Safety Variables

If there is more than one assessment at a visit (either due to multiple assessments or because an unscheduled or withdrawal visit assessment is mapped to a nominal visit with an already existing value) the value that will be used in summary tables by visit will be the one closest to the nominal day for the visit but prioritizing values from scheduled visits above values from withdrawal or unscheduled visits. In the ordering of multiple values, assessments without recorded time will come after assessments with recorded time and the first in the ordering will be picked.

Laboratory Tests and ECG

Assessments of laboratory tests and ECGs at unscheduled visits and withdrawal visits will be assigned to a nominal visit according to the visit windowing specified in [Panel 11](#) for participants in the APTS. Assessments for participants not receiving any infusions of IMP will be assigned to the Baseline Visit.

Panel 11 Visit Windows – Laboratory tests, ECG

Nominal Visit Number	Nominal Visit Week	Nominal Visit Day	Time Window
Visit 1 (Screening Visit)	-4	-28	Before day 0 and before first IMP infusion
Visit 2 (Baseline Visit)	0	0	Same day as first IMP infusion (Day 0) and prior to IMP infusion on that date
Visit 5	12	84	After start of first IMP infusion to start of Visit 5 IMP infusion
Visit 8	24	168	After start of Visit 5 IMP infusion to start of Visit 8 IMP infusion

Nominal Visit Number	Nominal Visit Week	Nominal Visit Day	Time Window
Visit 11	36	252	After start of Visit 8 IMP infusion to start of Visit 11 IMP infusion
Visit 14	48	336	After start of Visit 11 IMP infusion

Vital Signs

Vital signs will be assessed before and after infusion at nominal visits. For unscheduled or withdrawal visit assessments of vital signs, the values will be assigned a nominal visit according to [Panel 12](#), and for scheduled visits where no IMP was given the assessment will be windowed to the pre-dose assessment at the nominal visit.

Panel 12 Visit Windows – Vital Signs (Pulse rate, Blood Pressure, Temperature)

Nominal Visit Number	Nominal Visit Week	Nominal Visit Day	Time Window
Visit 1 (Screening Visit)	-4	-28	Before day 0 and before first IMP infusion
Visit 2 (Baseline Visit) pre-dose	0	0	Same day as first IMP infusion (Day 0) and prior to IMP infusion on that date
Visit 2 (Baseline Visit) post-dose	0	0	After start of first IMP infusion to day 42
Visit 5 pre-dose	12	84	Day 43 to start of Visit 5 IMP infusion
Visit 5 post-dose	12	84	After start of Visit 5 IMP infusion to day 126
Visit 8 pre-dose	24	168	Day 127 to start of Visit 8 IMP infusion
Visit 8 post-dose	24	168	After start of Visit 8 IMP infusion to day 210
Visit 11 pre-dose	36	252	Day 211 to start of Visit 11 IMP infusion
Visit 11 post-dose	36	252	After start of Visit 11 IMP infusion to day 294
Visit 14	48	336	> 294

Height and Weight

Height is only assessed at the screening visit and weight is assessed once at each nominal visit. Windowing of these parameters will follow the windowing used for Laboratory tests and ECG.

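### Panel 12 leaves Withdrawal Visit pulse, blood pressure and temperature from the first half of a dosing cycle out of the by-visit tables, while Panel 11 keeps labs, ECG and weight from the same visit

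*SAP*

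**What the plan says.** For vital signs, SAP 23.3.2 states: "For unscheduled or withdrawal visit assessments of vital signs, the values will be assigned a nominal visit according to" Panel 12. The panel covers pulse rate, blood pressure and temperature, and splits each infusion visit into a pre-dose and a post-dose row. The four post-dose rows read:

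- Visit 2: "After start of first IMP infusion to day 42"
- Visit 5: "After start of Visit 5 IMP infusion to day 126"
- Visit 8: "After start of Visit 8 IMP infusion to day 210"
- Visit 11: "After start of Visit 11 IMP infusion to day 294"

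If a visit has several values, the by-visit table takes the one nearest the nominal day, but "prioritizing values from scheduled visits above values from withdrawal or unscheduled visits".

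Panel 11, for laboratory tests and ECG, has no post-dose rows and carries values forward. Its Visit 8 window is "After start of Visit 5 IMP infusion to start of Visit 8 IMP infusion". The Height and Weight paragraph of 23.3.2 applies Panel 11 to weight. For scheduled visits without an infusion, 23.3.2 sends vital signs to the pre-dose row.

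Protocol 8.4 and 9.8 place the scheduled post-infusion vital signs after the end of infusion and before discharge. SAP 14.4 presents absolute values and changes from baseline by visit. SAP 14.2 uses every available assessment to evaluate PCS values.

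**The concern.** A Panel 12 post-dose row combines two different things: a reading taken on the infusion day to show acute effects, and any withdrawal reading over the next six weeks or so. Only one value per time point reaches the by-visit table, and the scheduled one is preferred. Anyone inside a post-dose window has started that infusion and should have the scheduled reading, so the withdrawal reading is normally displaced.

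Absolute values and changes from baseline in vital signs are among the primary endpoints (SAP 5, Panel 2). The readings displaced belong to people who leave soon after an infusion, who may include those leaving for tolerability. PCS criteria need large shifts, such as systolic pressure of at least 180 mmHg with a rise of at least 20 (SAP Appendix III, Table 2). The full-value listings in 14.2 cover only participants with a PCS value for that variable. A smaller change at a displaced Withdrawal Visit would therefore appear in no vital-sign table or listing specified in 14.2 or 14.4.

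**Working it through.** **Inputs.** Nominal infusion days 0, 84, 168 and 252, and Completion on Day 336 (Panel 12). Post-dose limits 42, 126, 210 and 294 (Panel 12). Visit window ±3 days for Visits 5, 8 and 11 (SAP Appendix IV). Planned N of 125 with 20% withdrawal (SAP 20).

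**1. The plan's limits.** Each is the midpoint of adjacent nominal days:

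- (0 + 84)/2 = 42
- (84 + 168)/2 = 126
- (168 + 252)/2 = 210
- (252 + 336)/2 = 294

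All four match, so the windows look deliberate.

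**2. Actual length.** Day 0 is the first infusion, so the first window is 42 days. For infusions 2 to 4 the limit is 42 days after the nominal day. With ±3 days it is 42 − 3 = 39 to 42 + 3 = 45 days after the actual infusion.

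**3. Share of the treatment period.** With infusions on nominal days, 4 × 42 = 168 of Days 1 to 335 fall in a post-dose row: 168/335 = 50%.

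**4. Tracing Withdrawal Visits** (infusions on nominal days, scheduled post-dose reading present):

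| Withdrawal Visit | Pulse, BP, temperature (Panel 12) | In by-visit table? | Labs, ECG, weight (Panel 11) |
|---|---|---|---|
| Day 30 | Visit 2 post-dose | No, displaced | Visit 5 |
| Day 42 | Visit 2 post-dose | No, displaced | Visit 5 |
| Day 43 | Visit 5 pre-dose | Yes | Visit 5 |
| Day 110 | Visit 5 post-dose | No, displaced | Visit 8 |
| Day 280 | Visit 11 post-dose | No, displaced | Visit 14 |
| Day 295 | Visit 14 | Yes | Visit 14 |

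The Panel 11 values are used in every row, because the participant has left before the next scheduled visit. For vital signs, moving from Day 42 to Day 43 decides whether the reading counts.

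**5. Scale (assumption).** Planned withdrawals are 125 × 0.20 = 25. The documents do not say when in a cycle withdrawals occur. If all 25 attend a Withdrawal Visit and a share *s* falls in the first half of a cycle, the number affected is 25 × *s*:

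- *s* = 0.25: 6.25
- *s* = 0.50: 12.5
- *s* = 0.75: 18.75

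The range is about 6 to 19 participants.

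**The case against.** The case for leaving Panel 12 alone is that midpoints assign a reading to the nearest visit, as Panels 8 and 9 do for the patient-reported scales. Day 110 is 26 days from Week 12 and 58 days from Week 24. Carrying readings forward can file one from the day after an infusion under a visit nearly 12 weeks later. That is a fair cost, but it does not settle the matter. Panels 8 and 9 have no post-dose row, so nearest-visit assignment there does not set a withdrawal value against an infusion-day reading. The SAP also already treats the pre-dose row as the place for scheduled vital signs not tied to an infusion.

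Several stronger readings are tempting, and the documents do not support them:

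- **The last reading of early leavers is lost.** Those who withdraw, except by withdrawing consent, are also asked to attend a Safety Follow-up Visit 20 weeks after the last infusion (protocol 6.2 and 8.7). Vital signs are scheduled there, and Panel 12 does not re-window scheduled readings. What drops out is the Withdrawal Visit reading.
- **Unscheduled readings are lost in general.** In a continuing participant, an unscheduled reading carried forward would normally be displaced by the next scheduled pre-dose value. It drops out under either rule.
- **Safety signals are missed.** PCS evaluation uses all assessments. Clinically significant vital signs are recorded as adverse events (protocol 9.6.1), and adverse events leading to withdrawal are listed and summarised (SAP 14.1.8).
- **The post-infusion column is unreliable.** A late reading appears there only if the scheduled post-dose value is missing, and that reading is mandatory before discharge.
- **A definite 12 or 13 participants are affected.** That figure needs full attendance and an even spread. Patients who withdraw consent may decline the visit, and those lost to follow-up count as withdrawn.

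**Conclusion.** The point holds in a narrow form. As written, Panel 12 and the priority rule together keep Withdrawal Visit pulse, blood pressure and temperature readings from the first half of a cycle out of the by-visit summaries. Panel 11 keeps the other safety data from the same contact, and Panel 12 itself keeps a reading taken one day past the limit. Mislabelling as post-infusion is possible but should be rare.

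The loss is one descriptive value per variable for each affected participant, perhaps 6 to 19 people under the attendance and timing assumptions above, and fewer with non-attendance. Weight and PCS evaluation are unaffected, no formal testing is planned, and a later follow-up reading is planned for those who attend. Priority: minor. It is still worth correcting, because data already collected for a primary-endpoint table are dropped by a rule that disagrees with the panel beside it.

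**What to change.** In Panel 12, limit each post-dose row to readings on the infusion day after infusion start. Assign later withdrawal and unscheduled pulse, blood pressure and temperature readings to the pre-dose row of the next nominal visit, or to Visit 14 after the fourth infusion, in line with Panel 11.

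This costs a few lines of SAP text and a small change to the windowing program, with no new data. For continuing participants the scheduled pre-dose value keeps its priority, so their tables do not change when that value exists. The downside is that some pre-dose summaries will include readings taken well before the nominal day, as the laboratory and ECG tables already do.

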23.4 Handling Missing or Incomplete Dates/Times

23.4.1 Withdrawal Date

Missing withdrawal dates will not be imputed and time to withdrawal from study or treatment will not be calculated for missing withdrawal dates.

23.4.2 Medical Disorder Start and Stop Dates

Incomplete dates will not be imputed. Classification of events into *concurrent medical disorders* or *past disorders* will be based on the reported ongoing status.

23.4.3 Medication Start and Stop Dates

Imputation of incomplete or partially missing dates will be performed in order to document the assigned categories specified in chapter [10](#).

The algorithm for imputing the start dates will follow the one used for imputing adverse event start dates, see section [23.4.4](#). Furthermore when the start date is completely missing for medications collected at the Screening Visit, the medication start date is imputed with the date of the Screening Visit.

For imputing stop dates, the following will apply, where UK and UKN indicate unknown or missing day and month, respectively:

- UK-MMM-YYYY: Medication end date is imputed with the last day of the month
- UK-UKN-YYYY: Medication end date is imputed with 31-DEC-YYYY
- If the stop date collected at the Screening Visit is completely missing and the medication is not being recorded as an ongoing medication, then the medication stop date is imputed with the date of the Screening Visit.

23.4.4 Adverse Event Start and Stop Dates

Imputation of partially or completely missing dates will be included in data in order to document the classification of the treatment emergent status and assignment of the adverse event to a period. For an adverse event with an imputed start date, the classification of treatment emergent will depend only on whether the imputed date is the same as the date(s) of infusion and not the timepoint of the infusion, since start times for adverse events will not be imputed. No duration will be calculated for adverse events with incomplete start-or-stop dates or for ongoing adverse events.

Imputation will follow the algorithm below. If an imputed start date after this procedure is after the end date, the start date will be set to the end date.

Start Dates

Participants with no IMP infusion

For participants who have not been treated, the imputation of AE start date will be performed as follows, where UK and UKN indicate unknown or missing day and month, respectively:

- UK-MMM-YYYY: The start date will be imputed with either the 1st of the month, or date of the Baseline Visit. Date of the Baseline Visit will be used if that is the later of the two and if it is within the specified month and year
- UK-UKN-YYYY: The start date will be imputed with either JAN 1, or date of the Baseline Visit. Date of the Baseline Visit will be used if it is within the specified year

If the AE start date is completely missing, it will be set equal to the date of the Baseline Visit.

Participants who received at least one IMP infusion

For participants, who have been treated, the imputation of AE start dates will be performed as follows:

- UK-MMM-YYYY:
 - If the year and month are equal to the year and month of treatment start date, the adverse event start date is imputed with the date of first dose of IMP
 - If the year is equal to the year of treatment start date: If the month is prior to the treatment start date, the adverse event start date is imputed with the last day of the month. If the month is equal to the month of the treatment start date, see above. If the month is after the month of the treatment start date, the adverse event start date is imputed with the first day of the month
 - If the year is prior to treatment start date, the adverse event start date is imputed with the last day of the month
 - If the year is after the year of treatment start date, the adverse event start date is imputed with the first day of the month
- UK-UKN-YYYY:
 - If the year is equal to the year of treatment start date, the adverse event start date is imputed with treatment start date
 - If the year is prior to the year of treatment start date, the adverse event start date is imputed with 31-DEC-YYYY
 - If the year is after the year of treatment start date, the adverse event start date is imputed with 01-JAN-YYYY
- DD-UKN-YYYY:
 - If the year is equal to the year of treatment start date, the adverse event start date is imputed with treatment start date
 - If the year is prior to the year of treatment start date, the adverse event start date is imputed with DD-DEC-YYYY
 - If the year is after the year of treatment start date, the adverse event start date is imputed with DD-JAN-YYYY

- If the AE start date is completely missing:
 - If the AE stop date is not missing and is before the treatment start date, the adverse event start date is imputed with the AE stop date
 - If the AE stop date is not missing and is after the treatment start date, the adverse event start date is imputed with the treatment start date
 - If the AE stop date is missing (either completely or partially), the adverse event start date is imputed with the treatment start date

End Dates

Missing AE end dates will not be imputed.

Incomplete Intensity Change Dates

If the day is missing in a date of intensity change for an adverse event, the date will be imputed using the same algorithm as described above for incomplete adverse event start dates.

If this results in an imputed start date that is after the end date of the original event or after an intensity change that comes after the intensity change in question, the start date will be imputed with the end date of the original event or the date of the later intensity or change.

23.5 Data with Multiple Records

23.5.1 Dose Changes in Medication

Dose changes in medications are recorded on multiple rows in the dataset, with different start and stop dates. When classifying medications into categories (see chapter 10), each dose is considered a separate medication, and the same medication can be assigned to several categories for the same participant. Within a category, multiple entries contribute as a single count.

23.5.2 Treatment-emergent AEs and Changes in Intensity or Seriousness of Adverse Events

An AE spans an interval in time, and in data it is potentially divided into several sub-intervals to ensure that within each sub-interval the status is the same for the whole interval. This could lead to multiple records for an AE as described in [Panel 13](#).

Panel 13 Definition of Multiple Records

Event	Details	TEAE flag
AE starts at or after first dose of IMP	AE event created (start and possibly stop dates and AE characteristics are described)	
 • TRTEMFL="Y"
Change in intensity	AE is split in 2 rows: Before and after change, so each part has the correct intensity	
 • If prior to first IMP => TRTEMFL = " " • If at or after first IMP AND intensity increase => TRTEMFL="Y" • If at or after first IMP AND intensity decrease => TRTEMFL = " "
AE becomes SAE	If an existing AE becomes an SAE the AE is split in 2 rows: Before and after the datetime of the SAE occurrence. The AE is marked as SAE from this point and onwards.	
 • If prior to first IMP => TRTEMFL = " " • If at or after first IMP => TRTEMFL="Y"

Events that do not happen simultaneously and with same precision on datetime, handle individually as above. Unknown time will be considered later than known time points.
 
For events where multiple changes occur that do not happen simultaneously, extra rows are added for each change; for instance, will an AE with an intensity change and a change in seriousness be split into 3 rows: 1 for the original AE when it starts, 1 for the intensity change and 1 for the serious change.
		
Events that happen simultaneously: SAE and change in intensity	An existing AE will be split in 2 rows: Before and after the event	
 • If prior to first IMP => TRTEMFL = " " • If at or after first IMP => TRTEMFL="Y" (due to SAE, regardless of the direction of the intensity change)

References

Appendix II

SAS® Code

SAS® Code

Short-term Efficacy Estimand

The SAS® code for the analysis of the short-term efficacy estimand described in Section 13.5.1 is given below. Here it is assumed that the ordering of the week factor is week 1, week 2, week 3, week 4, ...

```
proc mixed data=DPS2 method = REML noclprint;
  class COUNTRG1(ref = "OTHER") AVISITN USUBJID;

  model CHG = COUNTRG1 AVISITN LOGBASE LOGBASE*AVISITN / DDFM = KR;

  repeated AVISITN / type=UN subject=USUBJID;

  lsmeans AVISITN 'Change from Baseline in Weekly Attacks: Weeks 1-4'
    [1, 1] [1, 2] [1, 3] [1, 4] / divisor = 4;

run;
```

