13.5 Analysis Methodology for the Secondary and Exploratory Endpoints

13.5.1 Short-term Efficacy Estimand

The short-term efficacy estimand is the mean change from Baseline in the weekly number of attacks (Weeks 1-4) for participants with chronic cluster headache receiving IV infusion of eptinezumab 400 mg every 12 weeks, without the use of transitional treatment (GON block and oral steroids), and regardless of the use of abortive and preventive medication for cluster headache, and infusion interruption or termination before full dose is received.

Clinical Question of Interest

The clinical question of interest is changes in cluster headache symptoms within the first 4 weeks after infusion with eptinezumab 400 mg.

Attributes of the Short-term Efficacy Estimand

The short-term efficacy estimand has the following attributes:

- The **treatment condition of interest** will be IV infusion of eptinezumab 400 mg every 12 weeks, with or without the use of abortive and preventive medication for cluster headache
- The **population of interest** will be participants with cCH
- The **endpoint to be obtained to address the clinical question** is change from Baseline in the weekly number of attacks (Weeks 1-4)
- The **intercurrent event** use of transitional treatment will be addressed by a hypothetical strategy estimating the efficacy, in the hypothetical scenario where no transitional treatment is available, while interruption or termination of IMP such that full dose is not received will be addressed by a treatment policy strategy
- The **population level summary** will be the mean change across weeks 1-4

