13.5.1.2 Estimator

To estimate the change from Baseline in the number of weekly attacks (Weeks 1-4) described above, a Mixed Model for Repeated Measurements (MMRM) using a restricted maximum likelihood (REML)-based approach will be used. The data used for the MMRM is FAS and DPS2. The MMRM will include the following fixed effects: week (1, 2, 3, 4, 13, 14, 15, 16, 25, 26, 27, 28, 37, 38, 39, 40), and country (for details see section [23.2.3](#)) as factors, logarithm of the baseline score as a continuous covariate, and the logarithm of the baseline score-by-week interaction. An unstructured covariance structure will be used to model the within-participant errors. The Kenward-Roger approximation will be used to estimate denominator degrees of freedom. The change from Baseline in the number of weekly attacks (Weeks 1-4) will be estimated as the average from the least squares estimates from the MMRM for the week effect using the contrast [1, 1] [1, 2] [1, 3] [1, 4] /divisor = 4. The SAS® code for the analysis is shown in [Appendix II](#). If this analysis fails to converge the following covariance structures will be tried out:

- UN(15) - banded unstructured
- UN(14) - banded unstructured
- UN(13) - banded unstructured
- UN(12) - banded unstructured
- TOEPH – heterogenous Toeplitz
- CSH – heterogenous compound symmetry
- TOEP - Toeplitz
- CS - Compound Symmetry

and the one with the lowest AIC amongst the ones that converged will be applied. In case of no models converging, the results will only be shown as described in chapter [7](#).

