23.2.3 Country

Countries with at least 20 participants will be kept individually, and countries with less than 20 participants will be combined into one country called “other”.

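### In this single-arm trial the MMRM estimates weight country groups equally rather than by participants, which can widen the confidence intervals and shift the estimated mean change

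*SAP*

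**What the plan says.** SAP 13.5.1 sets the target: "The short-term efficacy estimand is the mean change from Baseline in the weekly number of attacks (Weeks 1-4) for participants with chronic cluster headache". The population-level summary "will be the mean change across weeks 1-4". Neither statement mentions standardising to any set of country weights.

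SAP 13.5.1.2 puts week, country, log baseline and log baseline by week in the MMRM. The Weeks 1-4 result is "estimated as the average from the least squares estimates from the MMRM for the week effect". Appendix II gives the model as "model CHG = COUNTRG1 AVISITN LOGBASE LOGBASE*AVISITN / DDFM = KR", declares the country variable in the CLASS statement, and requests the result with a line that begins "lsmeans AVISITN 'Change from Baseline in Weekly Attacks: Weeks 1-4". The only option on that line is the divisor of 4. No observed-margins or other weighting option appears in the text or the code.

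SAP 23.2.3 keeps countries with 20 or more participants as separate levels, while "countries with less than 20 participants will be combined into one country" called 'other'. No minimum size is set for that pool.

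The same estimator is reused for Weeks 1-2 (13.5.2), for Months 1-12 (13.5.3), for the continuous eDiary endpoints, SIS, EQ-5D-5L VAS, WPAI and PGIC (13.5.6.1), and in the MMRM sensitivity analyses in 13.5.9. SAP 13.5.7 says that country is in the model to account for country differences. The protocol's MMRM (section 16.8.2) has no country term, and SAP chapter 22 does not list its addition as a change.

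**The concern.** Without a weighting option, the least-squares mean for a week averages the country levels with weight 1/k each, where k is the number of levels. The SAP does not write this out; it follows from the software default. In a randomised comparison with an additive country effect, the weighting drops out of the treatment difference. Here there is one arm, so the least-squares mean and its 95% CI are themselves the efficacy result and carry the weighting directly.

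Two things are at stake. The first is precision: small groups get more weight than their information supports. The second is the quantity reported: an equally weighted average of country groups differs from the mean over participants when sizes are unequal and country means differ. The groups themselves are partly an artefact of the cut-off at 20. A country that recruits 20 instead of 19 participants becomes its own level and changes every weight.

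**Working it through.** **Inputs.** N = 125 treated (SAP chapter 20). It reproduces from the plan's own assumptions: 100 / (1 - 0.20) = 125. The documents give no participant numbers by country, so the splits below are assumed. The SE ratio depends only on the proportions in each group, not on the SD, and so changes little if the FAS is slightly smaller than 125.

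**SE ratio.** Let group j have n_j participants with equal residual variance s². The variance of a weighted mean of country means is s² × Σ w_j² / n_j.

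- Equal weights, w_j = 1/k: variance = (s²/k²) × Σ(1/n_j).
- Participant weights, w_j = n_j/N: variance = s²/N.
- Ratio of SEs = √(N × Σ 1/n_j) / k.

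| Assumed split of 125 | k | Σ 1/n_j | N × Σ 1/n_j | SE ratio |
|---|---|---|---|---|
| 25/25/25/25/25 | 5 | 0.2000 | 25.00 | 1.00 |
| 40/25/20/40 | 4 | 0.1400 | 17.50 | 1.05 |
| 50/30/20/25 | 4 | 0.1433 | 17.92 | 1.06 |
| 60/20/20/25 | 4 | 0.1567 | 19.58 | 1.11 |
| 85/20/20 | 3 | 0.1118 | 13.97 | 1.25 |
| 103/22 | 2 | 0.0552 | 6.90 | 1.31 |
| 60/40/20/5 | 4 | 0.2917 | 36.46 | 1.51 |

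**Shift in the estimate.** Shift = Σ (1/k - n_j/N) × c_j, where c_j is the country effect. It is zero if all sizes are equal, and zero if all c_j are equal.

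- 60/40/20/5, with the group of 5 as 'other': its weight is 1/4 = 0.25 against a share of 5/125 = 0.04. If 'other' differs from the rest by an assumed 2 attacks per week, the shift is (0.25 - 0.04) × 2 = 0.42 attacks per week.
- 60/20/20/25 with assumed effects 0, -1, -2, -3: the equal-weight average is -6/4 = -1.50 and the participant average is (-20 - 40 - 75)/125 = -1.08, so the shift is again 0.42 in size.

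The model has no country-by-week term. The shift is therefore the same in every week, and averaging over weeks does not reduce it.

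**Check in the repeated-measures setting.** A 16-week model with 20% dropout, an exchangeable correlation of 0.6 and the same fixed effects gave SEs of 0.493 (equal weights) and 0.449 (participant weights) for 60/20/20/25. That is a ratio of 1.10, against 1.11 from the formula. For five groups of 25 both SEs were 0.449. In a complete-data single-time-point version, the participant-weighted least-squares mean equalled the raw participant mean to rounding error.

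**The case against.** Text and code agree with each other, so this is not an internal contradiction. The estimand's population is people with chronic cluster headache, not the enrolled country mix, and recruitment is competitive between sites (protocol 5.2), so that mix is partly accidental. Including country has a stated reason. It stands that the SAP does not name participant weights as its target. But it does not name equal country weights either, and the reason in 13.5.7 supports adjusting for country, not weighting a residual pool like a large country.

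Descriptive means will be shown beside the model results. That helps only in part: SAP chapter 6 bases them on DPS1, which keeps the data that the short-term (DPS2) and long-term (DPS3) estimands exclude.

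A reader might infer that the trial's main result is wrong. The documents do not support that. The primary endpoints are safety endpoints, there are no key secondary endpoints, and nothing is formally tested, so no decision rule rests on these intervals. Response, conversion and remission endpoints are summarised as counts or descriptively and are untouched.

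A reader might also infer that the SE is always inflated, or that the estimate moves whenever countries differ. Both need unequal group sizes, and the shift needs country differences as well. Nothing in the documents shows that 'other' will be tiny; it gathers every country below 20 and could be large.

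**Conclusion.** The point holds in conditional form. As written, the estimator weights country groups equally, while the estimand is a mean for participants, and in one arm the difference does not cancel. The loss of precision is nil with equal groups, about 5% to 11% of the SE with moderate imbalance, and 25% to 31% for splits such as 85/20/20 or 103/22. It reaches about 50% only if 'other' is very small, as in 60/40/20/5. A shift of about 0.4 attacks per week in that split also needs an assumed difference of 2 attacks per week.

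All of these sizes rest on assumed country splits, equal residual variance and an additive country effect. They show the possible range and do not predict what will happen. The change is worth making because it is nearly free and affects every MMRM estimate.

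**What to change.** In SAP 13.5.1.2 and Appendix II, keep country in the model and request the contrasts with observed-margin weights based on FAS participants. One way is an OM reference data set with one row per FAS participant per scheduled week (or month for the monthly models). Because week is itself in the model, building the margins from scheduled rather than observed records keeps dropout from altering the country weights. Write the statement as LSMESTIMATE: the printed label and bracketed contrast do not belong to LSMEANS. Correcting the syntax alone would leave the equal weighting in place.

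Apply the same weighting to the MMRMs in 13.5.2, 13.5.3, 13.5.6.1 and 13.5.9, and list the added country factor in chapter 22.

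Dropping country would return to the protocol's model, but it is a different model that removes the adjustment SAP 13.5.7 gives as its reason. It should not be presented as equivalent.

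The cost is one option, one small reference data set and a sentence in the SAP. No new data are needed.
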